The primary objective of this study is to develop and pilot test an innovative cognitive self-management intervention for PwMS delivered via web-based video conferencing. Data derived from interviews will be used to guide the adaptation of Stuifbergen's 8-week Memory, Attention, and Problem-Solving Skills in MS (MAPSS-MS) intervention to be delivered via web-based video conferencing. The adapted MAPSS-MS intervention will be feasibility tested in small groups of PwMS. Outcome variables include: (1) neurocognitive function assessed using the NIH Toolbox®, a comprehensive set of psychometrically sound neuro-behavioral measures¹⁸ that quickly assesses cognitive functions using an iPad, (2) objective PA and sleep using Actigraph™ accelerometers, (3) self-reported sleep, depression, and fatigue using the Patient-Reported Outcome Measurement Information System (PROMIS), and (4) MS specific self-management using the Multiple Sclerosis Self-Management Scale (MSSM). Community-residing PwMS, age 21 to 70, will be recruited from Central Texas to participate in Phase 1 interviews (n=5) and Phase 2 pilot testing (n=20) of the adapted version of the 8-week MAPSS-MS cognitive self-management intervention emphasizing PA delivered via web-based video conferencing. In Phase 2 pilot testing (n=20), an intervention group (n=10) will be compared to an "enhanced usual care" control group (n=10).

Research Proposal

The specific aims are to:

Aim 1: (a) Conduct interviews with PwMS to gather data to guide the adaptation of a tailored, cognitive self-management intervention delivered via web-based video conferencing, (b) Develop an adapted version of the 8-week MAPSS-MS intervention guided by the analysis of the interview data.

Aim 2: Conduct a feasibility study of the adapted MAPSS-MS cognitive self-management intervention emphasizing PA using objective and self-report data from community-residing PwMS. Process outcomes include success with recruitment, ability to deliver the intervention using web-based video conferencing, and ability to measure study outcomes.

4. Procedures

Study Design

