Phase 1 interviews will be conducted by the PI at a location selected by the participant (e.g. home).

Phase 2 data will be collected by mail (U.S. Postal service) and in-person at a location of the participants' choice (e.g. home). Participants will remotely attend eight weekly 90-minute intervention sessions from a location of their choice (e.g., home) via a web-based video conference platform on their chosen device (computer, tablet, and/or smart phone).

Research Proposal

b. Resources

External funding from the Center for Transdisciplinary Collaborative Research in Self-Management Science (National Institute of Nursing Research, National Institutes of Health, Grant: P30 NR0115335: PI [name]) at The University of Texas at Austin, School of Nursing is anticipated to start 9/1/2017.

c. Study Timeline

The estimated completion time for this study is 15 months. Data collection will begin in October of 2017 and continue through September of 2018 or study completion. Data analysis will be conducted from June to August of 2018 with report writing occurring from September through November of 2018.

5. Measures

The following measures will be used to collect data on the effectiveness of the intervention at the two data collection points with the exception of demographic information and MS functional status measure, which are baseline-only measures.

Phase 1 Measures

Interview questions have been designed specifically for this project.

Phase 2 Measures

The following measures will be used to collect data on the effectiveness of the intervention. Contextual factors and MS functional status will be collected at baseline only; the remaining measures will be collected at baseline and 8-weeks post intervention.

- 1) Contextual Factors – A Demographic Information Sheet will be used to collect baseline information on a variety of demographic (age, gender, education, marital status, ethnicity) and disease characteristics that will be used to describe the sample.

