 - b. Executive Function (EF) and Attention - EF: capacity to plan, organize and monitor the execution of behaviors that are strategically directed in a goal-oriented manner. Focuses on: 1) Inhibition of automatic response tendencies that may interfere with achieving a goal, and 2) set shifting, or the capacity for switching among multiple aspects of a strategy or task. Attention: allocation of one's limited capacities to deal with an abundance of environmental stimulation
 - i. NIH Toolbox Flanker Inhibitory Control and Attention Test (EF and Attention) [3 minutes]
 - ii. NIH Toolbox Dimensional Change Card Sort Test (EF) [4 minutes]
 - c. Working Memory - The capacity of an individual to hold information in a short-term buffer and manipulate the information.
 - i. NIH Toolbox List Sorting Working Memory Test (7 minutes)
 - d. Processing Speed - The amount of time it takes to mentally process a set amount of information, or the amount of information that can be processed within a certain unit of time. It is a measure that reflects mental efficiency
 - i. NIH Toolbox Pattern Comparison Processing Speed Test (3 minutes)
 - ii. NIH Toolbox Oral Symbol Digit Test (3 minutes)
 - e. Episodic Memory - The acquisition, storage and retrieval of new information. It involves conscious recollection of information learned within a context.
 - i. NIH Toolbox Picture Sequence Memory Test (7 minutes)
- 5) Participant-Reported Outcomes - Assessed with the Patient-Reported Measurement Information System (PROMIS®) developed using Item Response Theory by the Patient Reported Outcomes Measurement System (PROMIS) and the Quality of Life in Neurological Disorders (NeuroQoL) measurement system that evaluates and monitors physical, mental, and social effects experienced by adults living with neurological conditions. Both systems were funded by the National Institutes of Health (www.NIHPROMIS.org). All individual PROMIS and Neuro-QoL SF instruments take less than 5 minutes to complete – approximately 35 minutes for this 7-measure battery
 - a. Self-Efficacy –
 - i. PROMIS Short Form v1.0 – Self-Efficacy for Managing Medications and Treatments (4-items) - Assesses confidence in managing medication schedules of different complexity. Items also assess managing medication and other treatments in challenging situations such as when traveling, when running out of medication, and when adverse effects are encountered.

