 - ii. PROMIS Short Form v1.0 – Self-Efficacy for Managing Symptoms (4-items) - Assesses level of confidence to manage/control symptoms, to manage symptoms in different settings (home, public place, an unfamiliar place) and

Research Proposal

- to keep symptoms from interfering with work, sleep, relationships or recreational activities.
- iii. PROMIS Short Form v1.0 – Self-Efficacy for Managing Daily Activities (4-items) - Assesses confidence in performing various activities of daily living (ADLs) without assistance. Items also assess exercise, sexual activities and managing activities in challenging situations (traveling, bad weather).
- b. Cognitive Function –
- i. Neuro-QoL Short Form v2.0 – Cognitive Function (8-items) - Assesses mental acuity, concentration, verbal and nonverbal memory, verbal fluency, and perceived changes in these cognitive functions. The extent to which cognitive impairments interfere with daily functioning, whether other people observe cognitive impairments, and the impact of cognitive dysfunction on quality of life are also assessed.
- c. Depression –
- i. Neuro-QoL Short Form v1.0 – Depression (8-items) - Assesses self-reported negative mood (sadness, guilt), views of self (self-criticism, worthlessness), and social cognition (loneliness, interpersonal alienation), as well as decreased positive affect and engagement (loss of interest, meaning, and purpose). Somatic symptoms (changes in appetite, sleeping patterns) are not included, which eliminates consideration of these items' confounding effects when assessing patients with comorbid physical conditions. Assesses depression over the past seven days.
- d. Fatigue –
- i. Neuro-QoL Short Form v1.0 – Fatigue (8-items) - Assesses self-reported symptoms, from mild subjective feelings of tiredness to an overwhelming, debilitating, and sustained sense of exhaustion that likely decreases one's ability to execute daily activities and function normally in family or social roles. Fatigue is divided into the experience of fatigue (frequency, duration, and intensity) and the impact of fatigue on physical, mental, and social activities. Assesses fatigue over the past seven days.
- e. Sleep Disturbance –

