Phase 2 - Participants in the intervention group will benefit by learning about MS self-management and strategies to potentially improve cognitive function. Participants in the “enhanced usual care” control group will receive an illustrated instructional booklet on PA for PwMS developed by the National Center on Health, Physical Activity and Disability (NCHPAD).

d. Risks

There is very minimal risk to participants. The anticipated risks for PwMS participating in this study are:

- 1) Breach of confidentiality and loss of privacy
- 2) Potential distress related to concerns about MS-related cognitive function and performance on cognitive testing
- 3) Physical injury (falling or tripping) and temporary increases in MS symptoms due to increased core body temperature (e.g., fatigue, numbness/tingling sensations, foot drop) that may be related to PA or environmental conditions

These risks are considered minimal and will be addressed in the study protocol. They will also be described in the consent form. Persons who participate in the study may already have concerns

Research Proposal

about their perceived cognitive function and this may be a source of distress. It is not expected that these risks will be greater than those experienced in living with the cognitive demands of everyday life. Although participants with self-reported major depressive disorder will be screened and excluded at the beginning of the study, participants with T-scores ≥ 60 ($1^+ SD$) on the PROMIS Depression instrument will be referred to their healthcare provider for further assessment and treatment.

Data and Safety Monitoring Plan

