Monitoring is done of all procedures to ensure that they conform to approved protocol including: ISM auditing 10% of cases for compliance with IRB requirements, conformance with informed consent requirements, verification of source documents, and investigator compliance. Procedures to protect the confidentiality of participant data include using unique confidential ID numbers to identify participant data in lieu of participants' names on all study documents. The key linking participants' names to the ID numbers will be kept separate from the data in a password protected electronic file stored on UTBox. UTBox cloud storage has been approved by the Information Security Office for use with Confidential (formerly known as Category I) university data, including HIPAA data. Data will be collected using individual interviews, surveys of standardized measures (MS Self-Management, PROMIS and NIH Toolbox), and actigraphy to minimize research-associated risk.

Frequency of Monitoring

All adverse events will be assessed continuously and immediately as discovered by the PI. Monitoring by the IRB is conducted at annual continuing reviews, whenever modification requests are considered, and upon receiving reports of adverse events from the investigator or others.

Research Proposal

Identifying, Reviewing, and Reporting Adverse Events and Unanticipated Problems

The PI will report adverse events to the ISM and the IRB (using the IRB Unanticipated Problem Report) in a timely manner, and to the NIH annually at the continuing review. NIH requires annual reports of adverse events in the Research Performance Progress Report sent to the NINR. All actions of the IRB in response to an unexpected event or adverse event will be reported to NINR along with any changes or amendments to the protocol requested by the IRB in response to these reports. Proposed change or amendments to the protocol must be requested first in writing to the IRB, which will then grant or deny permission to make the requested change or amendment.

e. Recruitment

Participants for Phase 1 will be recruited from individuals who participated in the PI's previous study, Effects of Physical Activity on Cognition in Persons with MS (IRB Study Number: 2014-02-0031), and indicated that they would be willing to be contacted about future studies. These individuals will be invited to participate in the interview about cognitive function, MS self-management and physical activity by letter signed by the PI.

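### Does the depression referral rule fail because it names a PROMIS form while the measures list holds only a Neuro-QoL depression form?

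*Protocol*

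**What the plan says.** Section 6d (Risks) of the Protocol sets one score-based referral rule: a participant with a T-score of 60 or more, glossed as one SD above, "on the PROMIS Depression instrument will be referred to their healthcare provider for further assessment and treatment".

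Section 5 (Phase 2 Measures, item 5) lists the self-report forms one by one. The depression entry is "Neuro-QoL Short Form v1.0 – Depression (8-items"). Fatigue, sleep disturbance and cognitive function are also Neuro-QoL forms. The forms titled PROMIS are the three on self-efficacy. The item opens with "Participant-Reported Outcomes - Assessed with the Patient-Reported Measurement Information System (PROMIS"), and the same sentence then adds "and the Quality of Life in Neurological Disorders (NeuroQoL) measurement system". It gives the total burden as "approximately 35 minutes for this 7-measure battery".

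Two other places use the PROMIS name alone. Section 3 (Purpose) lists among the outcomes "self-reported sleep, depression, and fatigue using the Patient-Reported Outcome Measurement Information System (PROMIS"). The Monitoring Procedures in the Data and Safety Monitoring Plan describe the surveys as "surveys of standardized measures (MS Self-Management, PROMIS and NIH Toolbox"), without mention of Neuro-QoL.

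On timing, section 5 states that, apart from the baseline-only items, "the remaining measures will be collected at baseline and 8-weeks post intervention". The SAP mentions neither the referral rule nor T-scores.

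**The concern.** Read word for word, the referral rule is tied to an instrument that is not in the measures list. A rule that depends on a form nobody fills in would never trigger. If staff used the Neuro-QoL score instead, a cut-off stated for one instrument might be applied to another. A T-score has meaning only against a reference population, and the documents neither name that population nor say that the two systems share one.

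Two things would be at stake. The first is participant protection: this is the only referral trigger in the Protocol that rests on a score, and the questionnaires are completed at home and mailed back, so it works only if staff score the right form. The second is outcome definition: sleep, depression and fatigue are called PROMIS measures in the Purpose section and are listed as Neuro-QoL forms in the Measures section.

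**Working it through.** **1. Could a PROMIS depression form be in the battery but missing from the list?** The inputs are the forms in section 5, item 5.

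| System in the form's title | Forms | Count |
|---|---|---|
| PROMIS | Self-efficacy for medications and treatments; for symptoms; for daily activities | 3 |
| Neuro-QoL | Cognitive function; depression; fatigue; sleep disturbance | 4 |

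Total: 3 + 4 = 7, which reproduces the stated number of measures. At the stated ceiling of 5 minutes per form, 7 × 5 = 35 minutes, which reproduces the stated time. An eighth form would give 8 × 5 = 40 minutes and would break both figures. So exactly one depression form is administered.

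**2. Which form does the rule point to?** Set side by side:

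- Section 3 assigns depression to PROMIS and names no specific form.
- Section 5, item 5 opens under the PROMIS name, brings in Neuro-QoL in the same sentence, and lists the single depression form beneath.
- The Monitoring Procedures call the survey battery PROMIS.
- Section 6d speaks of a PROMIS depression instrument.

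Three of the four places use PROMIS alone, and the fourth uses it as the leading label. In that usage the phrase in section 6d has only one candidate.

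**3. Is the cut-off consistent with its own gloss?** Assume the usual T metric (mean 50, SD 10), which the documents do not state. Then (60 − 50) / 10 = 1 SD, which agrees with section 6d. This shows internal consistency only. It does not show that the cut-off was chosen for this form, and the documents offer nothing to test that either way.

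**4. How many assessments could the label touch?** With 20 Phase 2 participants and two collection points, 20 × 2 = 40. This is an upper bound, because section 6d does not say at which time points the rule applies. It counts administrations of the form, not referrals that would be missed.

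**5. Does anything reach the analysis?** The version and item count of each outcome form are given only in section 5, and those entries do not conflict with one another. The SAP's ANCOVA and its internal-consistency check run on whatever forms were completed. The sample of 20 does not depend on the name.

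**The case for a change.** The best argument for acting is that section 5 itself keeps the two systems apart. It joins them with an *and*, speaks of both being funded, and titles every form by its own system. On that view, working out the intended form settles the name but leaves the metric open. The Protocol does not say whose standard deviation the gloss refers to, or that depression T-scores from the two systems can be interchanged. The independent safety monitor audits 10% of cases and would want a rule that names a form participants actually complete. The correction would cost a few words.

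Part of this stands. The names differ, the reference population is not stated, and the passages must be reconciled. The rest does not carry over into a fault in the plan. That the documents are silent on whether the metrics agree is not evidence that they differ, and the answer lies in scoring manuals outside these documents. To say that a cut-off has been moved from one instrument to another assumes that section 6d meant some other form, yet the battery contains no other depression form.

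The safety argument is also narrower than it looks. The distress named as a likely adverse event concerns cognitive function, not depression. Several safeguards do not depend on this label: the exclusion for major psychiatric disorder (section 6b), the screening out of self-reported major depressive disorder (section 6d), the list of mental health resources given to everyone at consent, and discussion with the safety monitor of anyone who reports distress (both in the Data and Safety Monitoring Plan).

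**Conclusion.** This is a clerical inconsistency, and no change to the design or analysis follows. The instrument name in section 6d does not match the title in section 5, and the Purpose section uses the same loose label for three outcomes. Because the 7 listed forms fill the stated 7-measure battery, only one depression score exists at each time point, and staff would reach the same form whichever label they read. The rule can be applied.

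The documents demonstrate no referral gained or lost out of at most 40 assessments, no difference in the outcomes collected, and no effect on the ANCOVA or the sample size. Sections 3, 5 and 6d must be reconciled so that the form and its T-score metric carry one name throughout; I take no position on which instrument or cut-off is right.

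The conclusion rests on two points: that the section 5 list is complete, which the count and the minutes both support, and that PROMIS is used as a label for the whole battery, which sections 3 and 5 and the Monitoring Procedures support. It would need another look only if scoring material outside these documents showed that the stated cut-off does not fit the form being given.

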Participants randomly assigned to the intervention group (n=10) will remotely attend eight weekly 90-minute intervention sessions from the location of their choice (e.g., home) via their chosen device (computer, tablet, and/or smart phone) using a web-based video conference platform. The 10 intervention participants will be divided into 2 cohorts of 4 to 6 persons each. Participants in the “enhanced usual care” control group (n=10) will receive an illustrated instructional booklet on Physical Activity for persons with MS developed by the National Center on Health, Physical Activity and Disability (NCHPAD).

The eight weekly educational classes, originally developed for the MAPSS-MS intervention, will be adapted for remote web-based delivery (Appendix A). Specific intervention content will be modified based on feedback from Phase 1 interviews and research team members. Content will provide educational information emphasizing PA and include: (1) information on MS self-management strategies incorporating PA, fatigue, mood, and sleep self-monitoring; (2) assessment of cognitive problems; (3) resources and barriers to self-management; (4) goal setting and self-monitoring; and (5) lifestyle changes to maximize cognitive health. Phase 2 intervention content will follow the PA guidelines specifically designed for persons with MS developed by The Canadian Society for Exercise Physiology (Ginis & Hicks, 2007). These guidelines promote fitness benefits for adults with MS who have mild to moderate disability through “30 minutes of moderate-intensity aerobic activity (e.g. walking, housekeeping, gardening) 2 times per week and strength-training exercises for major muscle groups 2 times per week” (Latimer-Cheung, Martin Ginis, et al., 2013, p. 1829). All sessions will emphasize maximizing cognitive function in MS and address the interrelated effects of PA and other self-management skills on cognitive function.

Post-intervention data (questionnaire booklets, NIH Toolbox Cognitive Battery, and accelerometry) will be gathered, using the methods described for baseline data collection, within 2 weeks of the final intervention class for those in the intervention group. Those in the control group will complete post-intervention data 8-10 weeks after baseline data collection.

a. Location

The research will be performed at the University of Texas at Austin, School of Nursing and at locations chosen by each participant (e.g., their home).

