An Independent Safety Monitor (ISM) is deemed the appropriate level of monitoring for the small size (N=20) and low level of risk in this pilot study. [name], Research Scientist at The University of Texas at Austin, School of Nursing has agreed to serve as the study's ISM. [name] has extensive expertise in the conduct of human subjects research, is independent of the study and available in real time to review and recommend appropriate action regarding adverse events and other safety issues. The ISM will meet with the PI to discuss the research protocol approved by the University of Texas at Austin Institutional Review Board (IRB) prior to initiating data collection and then annually thereafter, if the study lasts longer than one year. The ISM will be contacted by the PI in the case of any adverse events potentially related to the study; we consider physical injury (falling or tripping) and temporary increases in MS symptoms due to increased core body temperature (e.g., fatigue, numbness/tingling sensations, foot drop) related to physical activity and distress related to concerns about MS-related cognitive impairment to be the most likely adverse events related to the study. A list of Austin-area mental health resources will be made available to all participants at the time of obtaining consent. Participants who report feeling distressed at any time during the study will be discussed with the ISM. Adverse events, as well as unanticipated problems involving risks to participants, will be reported to the ISM and the University of Texas at Austin IRB by the PI in a timely manner. We will ensure that the National Institute of Nursing Research (NINR) Project Officer is informed of any actions taken by the IRB as a result of such adverse events.

Monitoring Entities

The ISM and the University of Texas at Austin IRB will review this research protocol, all procedures, and will provide oversight. Monitoring will be done by the PI, ISM, and the University of Texas at Austin IRB. The PI is responsible for submitting all necessary reports to the University of Texas at Austin IRB and NINR.

Monitoring Procedures

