The PI and RAs have been trained in procedures to respect the rights of human subjects. There will be a special focus on issues related to 1) protecting privacy and confidentiality for participants randomized into the intervention group who will meet remotely in small groups (4-6 persons) via a web-based video conference platform on their chosen device - computer, tablet, and/or smart phone; and 2) awareness of fatigue and potential distress (related to concerns regarding cognitive and physical performance). Confidentiality and privacy of potential participants will be preserved, as the individual must contact the principal investigator to express interest in the study and disclose their name and contact information.

Research Proposal

Confidentiality of the Data or Samples

- a. Phase 1: An electronic recorder (e.g., Sony IC recorder) will be used to make electronic audio files of Phase 1 interviews. Audio files will be deleted from the recording device when transferred to UTBox cloud storage. UTBox has been approved by the Information Security Office for use with Confidential (formerly known as Category I) university data, including HIPAA data. Audio files will be named using the participant's unique ID number and the date recorded; no identifying data will be included or recorded from individual participants. De-identified audio files will be transcribed by a professional transcription service. Audio files stored on UTBox will be destroyed after they have been transcribed and the transcriptions reviewed by the PI and RA.
- b. Phase 2: After receipt of the signed consent and verification of MS diagnosis forms, participants will be mailed: 1) the questionnaire packet to complete at home with instructions (e.g., to take breaks as often as needed); 2) a postage-paid, preaddressed envelope to return the completed questionnaire packet to the PI's research office at The University of Texas at Austin, School of Nursing. A trained RA, blinded to the participant's group assignment, will collect the NIH Toolbox measures using an iPad at baseline and 8-weeks (post-intervention) at a location (e.g. home) selected by the participant. Accelerometer data will be downloaded directly from each device onto the PI's password-protected computer.

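### No scheduled question on falls, injuries or symptom flares is described in either arm, and only the intervention arm has regular contact, so control events are more likely to go unrecorded

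*Protocol*

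**What the plan says.** In the Protocol, section 6d (Risks), the Data and Safety Monitoring Plan lists falls or trips, temporary symptom increases from raised body temperature, and distress about cognitive impairment as the most likely study-related adverse events. Under Frequency of Monitoring it states: "All adverse events will be assessed continuously and immediately as discovered by the PI". The later subsection on identifying, reviewing and reporting events deals with onward reporting and does not say how events are to be elicited.

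On distress, the plan says: "Participants who report feeling distressed at any time during the study will be discussed with the ISM". On onward reporting, one sentence has the PI contact the Independent Safety Monitor (ISM) about events that might be related to the study. A later sentence says that adverse events, with no such limit, "will be reported to the ISM and the University of Texas at Austin IRB by the PI in a timely manner".

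Contact differs by arm (section 4, Phase 2). Intervention participants "will remotely attend eight weekly 90-minute intervention sessions from the location of their choice". Controls receive an instructional booklet on physical activity, and then: "Those in the control group will complete post-intervention data 8-10 weeks after baseline data collection".

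None of the Phase 2 measures in section 5 is described as asking about falls, injuries or adverse events. The SAP does not mention adverse events.

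**The concern.** When events are found passively, the number found depends on how often someone who would record them is in touch with the participant. A fall mentioned in a weekly video session reaches the study team within days. A control who trips in week 3 has no described occasion to mention it until the post-intervention visit, and no question there is described that would prompt it.

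Controls are not unexposed. Their booklet also promotes physical activity, so a control's fall or heat-related flare could be study-related.

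Two things are at stake. First, control events may never come to light, and a caveat at reporting cannot recover them. Second, if events are later tabulated by arm, the count would lean against the programme, and a low control count could be taken for the background rate.

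**Working it through.** The plan states no event rate, capture rate or safety sample-size figure, so there is nothing to reproduce. The check has a textual part and an illustration.

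**Contact between the two assessments (Protocol, section 4).** Intervention: 8 sessions × 90 minutes = 720 minutes = 12 hours. Control: none described over 8-10 weeks (56-70 days).

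**What existing measures would catch (sections 5, 6d and 7).** Fatigue, depression and sleep disturbance are measured in both arms with seven-day recall; for fatigue, "Assesses fatigue over the past seven days". Seven days is 7/70 = 10% to 7/56 = 12.5% of the control interval. A depression T-score of 60 or more triggers referral, and staff are trained to be alert to fatigue and distress. Fatigue and distress are thus partly covered. Falls and injuries are not.

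**Illustration.** From the documents: n = 10 per arm. Assumed: the same true risk p in both arms (2%, 5% or 10% of participants affected), intervention capture ci = 90%, control capture cc = 60% or 30%.

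Expected difference in recorded participants = 10 × p × (ci − cc):
- p = 2%: 10 × 0.02 × 0.30 = 0.06 to 10 × 0.02 × 0.60 = 0.12
- p = 5%: 0.15 to 0.30
- p = 10%: 0.3 to 0.6

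Chance that at least one affected control goes unrecorded = 1 − (1 − p(1 − cc))^10, for cc = 60% and then 30%:
- p = 2%: 1 − 0.992^10 = 8%; 1 − 0.986^10 = 13%
- p = 5%: 1 − 0.98^10 = 18%; 1 − 0.965^10 = 30%
- p = 10%: 1 − 0.96^10 = 34%; 1 − 0.93^10 = 52%

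For the by-arm count, take independent Binomial(10, p·ci) and Binomial(10, p·cc). Each cell gives the percentage of trials in which the intervention arm shows more / the control arm shows more; the rest are ties.

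| True risk | Equal capture 90/90 | 90/60 | 90/30 |
|---|---|---|---|
| 2% | 14 / 14 | 15 / 10 | 16 / 5 |
| 5% | 25 / 25 | 29 / 18 | 33 / 9 |
| 10% | 33 / 33 | 41 / 23 | 50 / 12 |

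The equal-capture column is the reference. At 2% and 5% risk, most of the trials in which the intervention arm shows more would occur with equal capture too. At those risks the lean comes at least as much from fewer trials in which controls show more. A gap of two or more participants towards the intervention arm occurs in about 1%, 6% and 14-18% of trials at 2%, 5% and 10% risk, against 1%, 5% and 11% under equal capture.

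If sessions surface only 60% of events and controls 30-45%, the direction is the same and the lean smaller: 10-11% against 5-8% at 2% risk, 22-23% against 11-15% at 5%, and 33-37% against 15-22% at 10%.

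**The case against.** The strongest reply is proportionality. The protocol says "There is very minimal risk to participants" and justifies its level of monitoring by the small sample and low risk. It provides an ISM available in real time, IRB and NIH reporting, a depression referral rule, and research assistant visits to both arms at which events could be volunteered. No arm comparison is planned, and nobody could soundly read a background rate from 10 controls. This stands, and it limits the point to an inexpensive improvement. It does not answer the missed control events, which do not depend on any later comparison.

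Absence from the text is also weaker evidence than usual. The consent pages, Appendix A with the session content, and the questionnaire booklets themselves are not in the documents available. Consent wording may ask participants to report problems, but that would be spontaneous reporting rather than a scheduled question. The IRB may also hear of events from people other than the investigator.

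A reader might infer that every event, once known, reaches the ISM whatever its cause. The text is mixed: one sentence limits contact to potentially related events and others do not. If the narrower rule applies, a control's background fall might not be a target event, whereas the illustration counts all events.

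A reader might also infer that the trial's results are biased. They are not: the feasibility outcomes and the ANCOVA do not use adverse event counts, and case-by-case handling of known events is unaffected.

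**Conclusion.** The point holds as a gap in detection, clearest for falls and injuries. Following the plan as written gives passive discovery with eight described live contacts in one arm and none in the other, so lower capture in controls is a sound inference.

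Its size cannot be derived from the documents. Under the assumed rates (2-10% risk, equal in both arms; 90% capture against 30-60%), the expected difference is 0.06 to 0.6 participants, below one in every scenario. The chance of leaving at least one affected control unrecorded runs from 8% to 52%. It would be tempting to read any excess in the intervention arm as caused by unequal contact, or to say that the programme will look harmful. Neither is supported: at 10 per arm much of any imbalance would be chance, and at low risk ties are the usual result.

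This is worth acting on because the remedy is inexpensive and missed events cannot be recovered. It does not threaten the trial's stated aims.

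**What to change.** 1. Add one identically worded page to the existing post-intervention booklet in both arms. Ask about any fall, trip or injury, any temporary increase in MS symptoms, and any distress about cognition or testing, each as yes/no and number of times. The window should be the time since the baseline visit. A fixed eight-week window would miss up to 2 of 10 weeks (20%) for controls assessed at week 10. The page goes back to the PI's office with the rest of the booklet, so the blinded research assistant need not see it.
2. Keep PI discovery as the real-time safety route, and record how each event was found (session, spontaneous report or booklet).
3. If events are reported by arm, use the booklet item descriptively and without a test. List PI-discovered events separately and state the unequal contact.

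The cost is one page, a few minutes per participant, PI review of returned pages and an IRB amendment. Recall over 8-10 weeks is imperfect in people enrolled for cognitive concerns (a Perceived Deficits Questionnaire score of at least 10). Only the intervention arm is taught self-monitoring, so some lean will remain. If the page captured 75% against 65% (assumed), the expected difference would be 10 × p × 0.10 = 0.02 to 0.10 participants. The intervention arm would show more in 24% of trials and the control arm in 20% at 5% risk, and in 34% against 28% at 10%. The bias is reduced, not removed, and a single end-of-study page protects nobody in real time.
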